Subjects will consist of a convenience sample of emergency department patients that require US-guided IV access. Eligible patients must be greater than 18 years old, and be self-identified as a difficult stick. The patient must also recount a prior emergency room visit or hospitalization in which more than 2 attempts were required to obtain access, have a history of a rescue catheter as the result of an inability to obtain a peripheral IV, or have one of the following conditions: end-stage renal disease on hemodialysis, IV drug abuse, or sickle cell disease.

Patients are excluded if they do not meet inclusion criteria, have participated in the study prior, have already undergone an attempt at vascular access or if the enrollment process has the potential to delay their care. Study participation is voluntary and written informed consent will be obtained. See Appendix A for Eligibility Checklist.

Numerous emergency room staff members are proficient in placing ultrasound-guided IVs. This includes physicians, nurses, and technicians. Staff will be enlisted on a voluntary basis to perform insertions on a voluntary basis.

Study Procedure:

Initial Assessment

Post-consent, eligible patients will be randomly allocated to the experimental group (forearm) or the control group (upper arm) in a ratio of 1:1 via a computer-generated randomization schedule. Research staff at the Department of Biostatistics will perform concealed immediate assignment by following a block scheme. Sealed envelopes containing the randomized IV access arm will be revealed at the bedside.

After patient enrollment, the insertion nurse or physician is engaged to perform the procedure. Only providers that are credentialed in ultrasound-guided vascular access will place catheters in study subjects. Vessel depth and diameter are measured by research staff and images are saved and archived for review by the Emergency Ultrasound Director. Vessel depth is measured on the ultrasound unit from the point of contact to the middle of the vein. All catheters are 20 gauge in diameter. The research staff will direct the inserter to choose the basilic, cephalic or brachial vein at least 2 cm above the antecubital fossa. If the patient is randomized to the control group, the inserter will place the Standard Long 4.78 cm catheter. If the patient is randomized to the experimental group, the inserter will place the Ultra Long 6.35 cm IV.

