Staff members are expected to attempt a minimum of 3 attempts before enlisting another provider for help. A functional IV is confirmed by extraction of 5 mL of nonpulsatile blood and low-resistance infusion of a 5 mL normal saline flush without evidence of extravasation. Other data variables collected include: inserter details, need for rescue inserter, patient pertinent medical history, vitals, age, sex, first-stick success, cannulation success or failure, vein diameter, catheter in vein longitudinal measurement, angle of insertion, number of venous access attempts, time of IV insertion, time to IV insertion, location of IV insertion, distance of IV insertion from the antecubital fossa, medications infused, ionic contrast injection for computed tomography. A venous access attempt is defined as each time the needle punctures the skin. Once the IV is secured, research staff will measure distance from the puncture or catheter insertion site to the antecubital fossa to quantify the site to antecubital measurement. See Appendix B for Data Collection Tool for insertion-related variables.

Follow-up Assessment

After initial assessment, the catheter will be assessed by the research team every 24 hours as long as the patient is hospitalized. At each follow up interval the researcher notes the date/time of evaluation and assesses for any signs and symptoms of complications and functionality of the device. A catheter is functional if the IV flushes without resistance. Catheters will be assessed daily for signs and symptoms of complications. See Appendix C for details regarding the assessment for functionality and complications. Any signs or symptoms of complications or lack of functionality will be reported to the patient's primary care team so that management of the IV catheter can be addressed.

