Beaumont Health is Michigan's largest health care system and is the most preferred for health care in the tri-county area, according to National Research Corporation survey data. A not-for-profit organization, it was formed in 2014 by Beaumont Health System, Botsford Hospital and Oakwood Healthcare to provide patients with the benefit of greater access to extraordinary, compassionate care, no matter where they live in Southeast Michigan. Beaumont Health has total net revenue of \$4.5 billion and consists of eight hospitals with 3,429 beds, 187 outpatient sites,

nearly 5,000 physicians, 38,000 employees and 3,500 volunteers. In 2017, Beaumont Health had 175,700 inpatient discharges, 17,800 births and 575,000 emergency visits.

Potential Impact:

Optimization of peripheral vascular care is a critical strategy to improve patient outcomes and reduce health care costs. Enhanced dwell times will lead to improved patient/staff satisfaction, decreased interruptions in care with shorter hospital length of stay, and decrease in complications such as thrombosis, bleeding, and infection. Over 2 billion IV catheters are used worldwide annually with less than one-third of catheters actually ending up in a patient. No other industry would accept this degree of failure in its most essential and necessary process to deliver care. In a study by Rickard et al in 2012, a patient required an average of 1.7 IV catheters per admission.¹⁵ With a cost of approximately \$35 per catheter for straightforward insertions, even a slight improvement in dwell time has the potential to save our health system millions of dollars.

References

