Appendix A: Eligibility Checklist

MRN: _____

Enrollment Date: ____/____/201____ Enrollment Time: ____:

Inclusions: All must be “yes” or do not enroll participant	Yes	No
Patient self-reports a history of difficult IV access		
Patient has a history of AT LEAST ONE of the following: (indicate which patient meets)		
Pt. recounts a prior emergency room visit/hospitalization when > 2 sticks required to obtain access		
History of a rescue catheter (such as US-guided IV, PICC line, midline, or CVC) ESRD on dialysis		
History of IV Drug		
Use History of Sickle Cell		
Patient is 18 years of age or older		

Exclusions: All must be “no” or do not enroll participant	Yes	No
Patient is under the age of 18 years of age		
Patient refuses to participate in the study		
Previous Inclusion in the study		
Cognitively impaired		

Form Completed by: _____ (Printed name) _____ (Signature)

Date: _____ Time: _____

Principal Investigator: _____ (Printed name) _____ (Signature)

Date: _____ Time: _____

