Appendix B: Insertion-Related Data

Research Staff completing form (signature/date): _____

Catheter Type (circle): Ultra Long IV Standard IV

	Depth (cm)	Diameter (cm)	# Attempts	Depth (cm)	Diameter (cm)	# Attempts
	1 st Venous Access point				2nd Venous Access point	
Inserter #1 ID:						
	1 st Venous Access point				2nd Venous Access point	
Inserter #2 ID:						

[figure not shown]
Minutes for procedure completion (time from needle to skin to dressing site): _____

Time at Completion of Insertion: _____

Initial EC Vitals: BP _____ HR _____

Gender: _____ Age: _____ BMI: _____

Location of Successful Cannulation
(Mark 1/2/3 for access attempts, circle successful site): Left Right

Insertion site distance from AC fossa (cm): _____

Disposition (Circle): Observation Regular Progressive ICU Discharge

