Appendix C: Functionality and Complications

Day	Functional 1: draw 2: flush 3: infusing 4: failed	Removal Time	Reason for Remov al	Venous Doppler 1: + for dvt 2: + for svt 3: + for dvt/svt 4: - for both 5: none	Lab confirmed infection Y/N	Discharge <24 hrs from insertion	Replacement Access in the case of failure 1: Midline 2: PICC 3: PIV 4: US PIV 5: CVC	Research staff initials
1								
2								
3								
4								
5								
6								
7								
8								
9								
10								
11								
12								
13								
14								
15								
16								
17								
18								
19								
20								
21								
22								
23								
24								
25								
26								
27								
28								
29								
30								

Reasons for Removal: (1) Completion of therapy; (2) infiltration; (3) infection; (4) dislodgement; (5) leaking; (6) pain; (7) other; (8) unknown

Post processing data

Angle of Insertion (°)	Length in vein (cm)	% Length in Vein

Signature/Date: _____

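### Eligibility does not ask for an expected stay, so patients sent home early can be randomised although they add very little to the catheter-survival comparison

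*Combined protocol and SAP*

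**What the plan says.** Study Population and Eligibility defines the source population: "Subjects will consist of a convenience sample of emergency department patients that require US-guided IV access". Entry depends on age and a history of difficult access: "Eligible patients must be greater than 18 years old, and be self-identified as a difficult stick", plus one of several supporting histories. The exclusions are failure to meet those criteria, earlier participation, and patients who "have already undergone an attempt at vascular access or if the enrollment process has the potential to delay their care". The Appendix A checklist opens with "Patient self-reports a history of difficult IV access" and adds refusal and cognitive impairment as exclusions. Neither place mentions admission, observation or expected need for access.

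After insertion, "the catheter will be assessed by the research team every 24 hours as long as the patient is hospitalized" (Follow-up Assessment). The forms expect some participants to go home. Appendix B has "Disposition (Circle): Observation Regular Progressive ICU Discharge", and Appendix C has a column headed "Discharge <24 hrs from insertion".

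Three other places bear on these patients:
- Study Design removes from the survival analysis those discharged with a functional catheter of under 24 hours' duration.
- Follow-up Assessment records the discharge time and takes the catheter as working up to then, unless the chart says otherwise.
- Statistical Analysis censors catheters that have not failed.

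Sample Size and Power Analysis gives 91 per group (182 in total) as a minimum. It assumes a 30-hour control median, a hazard ratio of 0.63, 80% power on the log-rank test and 10% dropout.

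**The concern.** The study title speaks of long-term survival, the background argues from the needs of hospitalised patients, and catheter checks stop when the hospital stay ends. Yet a patient likely to go home within hours meets every entry criterion. The plan then discards that patient's catheter from its main analysis if it is still working.

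Two things are at stake. The first is information: a short observation shows few failures, and the sample size states no early-discharge rate. The second is bias. The exclusion acts after randomisation and depends on outcome, because an early failure stays in the analysis while a working catheter leaves it. The more early discharges are enrolled, the more this rule operates. Changing the analysis removes the bias but does not supply the missing failures; only enrolment (or a larger sample) can do that.

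**Working it through.** **Inputs.** From Sample Size and Power Analysis: control median 30 h, hazard ratio 0.63, power 80%, 182 patients, 10% dropout. From Study Procedure: 1:1 allocation. From Statistical Analysis: significance level 0.05. Assumed here: a two-sided test and a constant hazard, λ = ln 2 / 30 = 0.0231 per hour in the control arm and 0.63λ in the experimental arm.

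**1. The plan's 182.** Schoenfeld's formula gives 4(1.960 + 0.842)² / (ln 0.63)² = 147.1, so 148 events; Freedman's gives 153. After 10% dropout, 182 × 0.90 ≈ 164 patients remain, so 148/164 = 90% must fail under observation. The average event probability by time T is 1 − ½[exp(−λT) + exp(−0.63λT)], which reaches 90% at about T = 132 h (5.5 days). Inflating for 10% dropout, T = 120 h requires 187 patients and T = 144 h requires 179. The plan states no observation time, so 182 can be reproduced only on the condition that catheters are observed for about 5 to 6 days.

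**2. What a short stay contributes.** The control failure probability is 1 − exp(−λT):
- 8 h: 1 − exp(−0.185) = 17%
- 72 h: 1 − exp(−1.664) = 81%

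The 8 h discharge time is an illustration, not a figure from the plan. In the experimental arm at 8 h it is 1 − exp(−0.63 × 0.185) = 11%. Under the Study Design rule, about 83% of control and 89% of experimental patients going home at 8 h would be removed, and all those left from this group would be failures.

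**3. Power if a share q of 182 is excluded.** Events D = 182(1 − q) × 0.902; power = Φ(|ln 0.63|√D / 2 − 1.960). The last two columns of power and sample size below show what happens with no other loss and with a further 10% dropout.

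| q | Events, no other loss | Power, no other loss | Power, further 10% dropout | Randomised to keep 164, no other loss |
|---|---|---|---|---|
| 10% | 147.8 | 80% | 76% | 183 |
| 20% | 131.4 | 75% | 71% | 205 |
| 30% | 115.0 | 70% | 65% | 235 |
| 40% | 98.5 | 63% | 59% | 274 |

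The final column is 164/(1 − q), rounded up. The excluded catheters are by definition still working, so keeping them as censored adds time at risk but no events. Censoring corrects the bias and leaves the event count as in the table.

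**The case against.** The strongest reply is that enrolling every difficult-access emergency patient is a reasonable pragmatic choice. It matches who receives these catheters, and early-discharged patients fully inform placement success, first-stick success, number of attempts and time to insertion. That stands for the placement objectives. It carries less weight for the primary one, because the plan's own survival analysis already leaves most of these patients out.

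A second reply is that the team foresaw early discharge, as the forms and the exclusion rule show. It did, but foreseeing the loss did not lead to a stated rate, a replacement rule or an entry criterion.

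A third is that enrolment comes before any access attempt and must not delay care, so disposition may be unknown. This is a real limit on the fix, and the proposed wording allows for it.

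Four stronger readings are tempting but unsupported:
- *That these catheters cannot inform survival at all.* Failures before discharge are counted, about 17% of controls by 8 h in the illustration.
- *That 182 is a fixed number of places being used up.* It is described as a minimum, and nothing caps enrolment.
- *That the primary objective itself is about long-term survival.* That term is in the title; the objective refers only to survival of the catheter.
- *That the site figures give the early-discharge rate.* Study Site says "In 2017, Beaumont Health had 175,700 inpatient discharges, 17,800 births and 575,000 emergency visits", and 175,700/575,000 = 31%. This is a system-wide ceiling on visits ending in inpatient admission. It leaves out observation stays and is not specific to patients needing ultrasound-guided access.

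**Conclusion.** The point holds as a gap between who is randomised and what the primary analysis can use. Early-discharged patients add very little to the survival comparison, and the present exclusion handles them by a rule that depends on outcome.

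The size of the loss is unknown, because the documents give neither an early-discharge rate nor an observation time. If exclusions stay at 10% and nothing else is lost, power remains near 80%. At 20% to 40% it falls to between 75% and 63%, or between 71% and 59% with a further 10% dropout. These figures assume a constant hazard, a two-sided 0.05 test, a 90% event probability among those analysed, and no replacement. A reader might infer that the trial is underpowered; the documents do not establish that. They show that nothing in the plan protects against it.

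**What to change.** 1. Add one inclusion line to Study Population and Eligibility and to Appendix A, completed before the envelope is opened and only where it does not delay care: *Treating team expects admission or observation with IV access needed for at least 24 hours.*
2. Replace the 24-hour exclusion in Study Design. Keep every randomised patient with a placed catheter in the survival analysis, censored at discharge if the catheter is functional, whatever the actual stay. This agrees with Follow-up Assessment and Statistical Analysis as already written.
3. In Sample Size and Power Analysis, state the early-discharge rate and observation time assumed for 182.

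The cost is an amendment covering an eligibility line, the checklist, the analysis population and the sample-size text. Recruitment would be somewhat slower, which looks manageable with about 10 ultrasound-guided catheters placed daily at the site. Some dispositions will be mispredicted or unknown at enrolment, and placement results will apply to patients expected to stay.

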A variable that may alter the survival of US-guided IVs that has not been studied extensively is the length of catheter that resides in the vein. Currently the general accepted rule is that an "adequate" amount of the catheter should be in the vein to avoid failure of the catheter.¹¹⁻¹⁴ However, this recommendation is only anecdotal and there has been no study to verify or quantify it. Our preliminary data focused on defining this relationship. In our study, **100% of catheters failed** in which less than 30% of the catheter was placed within the vein and **no failures** in those IVs in which at least 65% of the catheter was in the vein. All catheters in this analysis were commonly available 4.78 cm IVs. A key challenge for inserters is that achieving this quantity of catheter length in vein is impractical at the recommended angle of insertion when considering deeper target vessels. For many institutions, including ours, the 4.78 option is the longest stocked IV catheter and catheter survival is negatively impacted.

Central Hypothesis/Objectives:

We hypothesize that using an Ultra Long IV (6.35 cm) catheter increases the likelihood of ensuring a higher quantity of the catheter in the vessel lumen and leads to improved catheter longevity.

Primary Objective: Compare the IV survival between the Ultra Long IV (UL IV) (6.35 cm/20G) and the Standard Long IV (SL IV) (4.78 cm/20G) placed under US-guidance.

Function is defined as ability of catheter to flush 5 mL without resistance with or without blood sampling.

Secondary/Tertiary Objective(s):

Determine catheter survival based on vein depth.

Determine optimal cutoff length of catheter in vein for best survival profile.

Determine catheter survival based on angle of insertion.

Quantify specific etiologies related to premature catheter failure comparing UL IV to the SL IV.

Quantify overall costs associated with placement of the UL IV compared to the SL IV.

Determine overall success of placement UL IV versus SL IV.

Determine first-stick success UL IV compared to SLIV.

Determine number of attempts and time to insertion comparing UL IV to SL IV.

Safety Endpoint(s):

Compare phlebitis and thrombosis complication rates between the Ultra Long IV and the Standard Long IV.

[figure not shown]
Compare infection rates for all catheters.

Study Design:

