We propose a prospective, single-site, parallel, two-arm randomized investigation of catheter survival when two catheter lengths are evaluated. Specifically, experimental ultra long IV (6.35 cm/20G) will be compared with conventional standard long IV (4.78 cm/20G). The primary objective of this study is to demonstrate that there is better IV survival when the quantity of catheter residing in the vein is enhanced. Patients with functional catheters less than 24 hours duration and discharged will be excluded from the survival analysis. Exploratory secondary and tertiary objectives and adjusted multivariable analyses on the primary objective will also be conducted.

Preliminary Data:

[figure not shown]
We prospectively enrolled 86 patients in our study and performed IV assessment after IV placement and within 24 hours, 48 hours, and 72 hours from time of IV placement to assess for functionality. The graph below highlights percent of the catheter in the vein as it relates to IV failure.

The table below highlights key study findings of statistical significance.

Percent catheter in vein versus longevity	IV Functional N=57	IV Failed N=29	p-value
Percent catheter in vein	Survival	Failure	
<30%	0/6 (0%)	6/6 (100%)	<0.0002
30-64%	48/71(67.6%)	23/71(32.3%)	
≥65%	9/9 (100%)	0/9 (0%)	

In our pilot study, **100% of catheters failed** in which less than 30% of the catheter was placed within the vein and **no catheters failed** in those IVs in which at least 65% or 3.1 cm of the catheter was in the vein. It is therefore our goal to place at least 3.1 cm of the catheter in the vessel lumen. To accomplish this task, a calculation can be performed to determine the minimum total catheter length that should be utilized to cannulate a vein at a specific depth. The figure below illustrates this calculation, which is based on the Pythagorean theorem. Given that the depth of the vein is a known variable, it is possible to determine the appropriate total catheter length required prior to starting the procedure to ensure that at least 3.1 cm of the catheter can be placed inside the vein. Based on this hypothetical model, it is possible to achieve the target catheter in vein length for depths less than or equal to 1.20 cm using the 4.78 cm option. Any depth greater than 1.20 cm would require a longer catheter. A key assumption is that inserters approach the target vein with a 45 degrees angle of insertion.

Study Population and Eligibility:

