Appendix E represents the data collection documentation tool for all medications.

SVT and DVT rates will be calculated based on upper extremity proven diagnosis of SVT and/or DVT in symptomatic cases. Researchers will review all study subject records in EPIC and screen for all upper extremity venous Doppler examinations. Radiology interpretations will be reviewed for findings of consistent with thrombus. This review will occur thirty days post patient discharge.

Infection rate will be tracked using confirmed blood stream infection data from epidemiology. These are cases in which line sepsis or bacteremia is confirmed by positive blood cultures.

Cost difference between approaches will be tracked. Equipment costs and personnel costs will be tracked. Number and type of IV catheters inserted/attempted will be extracted from the medical record. Supply costs will be estimated based on number of IVs attempted. Median time to successful catheter placement will serve as a baseline for estimating time needed for future reinsertions. Time will be assigned a monetary value. We will also track the number of patients from each group that require a PICC or CVC as a rescue catheter.

Sample Size and Power Analysis:

For this randomly allocated two-groups experiment, the primary outcome is catheter survival. Sample size calculation is based on primary outcome: composite or all cause premature removal due to complication of the IV catheter. Based on literatures and a new published article immediately prior to study period, we estimate sample size using the median survival time 30 hours for the 4.78 cm standard IV option. 91 subjects per group for a total sample size of 182 subjects is the minimum recommendation assuming a 10% dropout rate. This calculation

achieves power of 80% to detect a hazard ratio of 0.63 or less for line failure of the 6.35 cm ultra long IV based on log-rank test.

Statistical Analysis:

Characteristics of enrolled and eligible patients will be summarized between two arms using means [standard deviations] and medians [interquartile ranges] compared by t-tests or Wilcoxon tests for continuous variables and frequencies (percentages) compared by chi-squared tests or Fisher's exact tests for categorical variables.

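### The allocation sentence names the randomised groups by insertion site (forearm or upper arm), but the rest of the plan randomises catheter length and directs every insertion to the upper arm

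*Combined protocol and SAP*

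**What the plan says.** Under Study Procedure, Initial Assessment, the allocation sentence is: "eligible patients will be randomly allocated to the experimental group (forearm) or the control group (upper arm) in a ratio of 1:1". The same paragraph ends with the concealment step: "Sealed envelopes containing the randomized IV access arm will be revealed at the bedside".

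The following paragraph gives one site instruction, not tied to either group: "The research staff will direct the inserter to choose the basilic, cephalic or brachial vein at least 2 cm above the antecubital fossa". It then defines the two arms by device: "If the patient is randomized to the control group, the inserter will place the Standard Long 4.78 cm catheter", and "If the patient is randomized to the experimental group, the inserter will place the Ultra Long 6.35 cm IV".

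Elsewhere the comparison is by length only. The Primary Objective and the Study Design both set the 6.35 cm catheter against the 4.78 cm catheter. The Sample Size and Power Analysis is built on a "hazard ratio of 0.63 or less for line failure of the 6.35 cm ultra long IV". The group field on the Appendix B form offers only the two catheter types. No other section assigns a group to the forearm.

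**The concern.** This is the only sentence in the plan that states the allocation rule, and it names a different factor from the one the trial is meant to test. It also conflicts with the site instruction in the next paragraph.

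If the labels reached the schedule, the envelopes or the bedside, Ultra Long catheters would go into the forearm while Standard Long catheters stayed in the upper arm. The Background/Scientific Rationale lists more distal placement in the arm among the features that lengthen the life of ultrasound-guided catheters. On the plan's own account, the error would therefore favour the experimental device on the primary outcome. If site followed arm completely, no regression adjustment could recover the effect of length. The Statistical Analysis section refers to Cox models for catheter variables and does not name insertion site as a covariate.

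**Working it through.** The point depends on the text, and the plan gives no figure to reproduce. The statements that define the groups or the site are set side by side below.

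| Where | Experimental | Control |
|---|---|---|
| Initial Assessment, allocation sentence | forearm | upper arm |
| Initial Assessment, site instruction | 2 cm or more above the fossa | the same |
| Initial Assessment, device sentences | 6.35 cm | 4.78 cm |
| Primary Objective | 6.35 cm | 4.78 cm |
| Study Design | 6.35 cm | 4.78 cm |
| Power statement | 6.35 cm | 4.78 cm |
| Appendix B, catheter type | Ultra Long | Standard |

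1. **Label against site instruction, experimental arm.** The forearm is below the antecubital fossa and the instruction requires a site above it. Both cannot be met.

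2. **Label against site instruction, control arm.** The upper arm is above the fossa. Both can be met, so the conflict falls on the experimental arm alone.

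3. **Label against length definition.** The two are not strictly incompatible, since a group could differ in both site and length. But the label names a factor that no objective or analysis compares between arms.

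4. **Envelope sentence.** Its phrase for the assignment may simply mean study arm. It does not say whether length or site is printed inside, so it does not settle the matter.

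5. **How many patients.** The plan has 182 patients, 91 per arm, including the 10% dropout allowance. Those whose label cannot be met together with the site instruction are 91/182 = 50% of the total, that is 91/91 experimental and 0/91 control.

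6. **Bounds on imbalance.** Let f be the share of experimental insertions that follow the label. The plan gives no value for f, so it is an assumption. The between-arm difference in forearm placement is then f − 0 = f.
   - f = 0 (site instruction governs): 0/91 v 0/91, a difference of 0 percentage points.
   - f = 0.50: 0.50 × 91 = 45.5, about 46/91 v 0/91, a difference of about 50 points.
   - f = 1 (labels govern): 91/91 v 0/91, a difference of 100 points.

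7. **Effect on the hazard ratio.** The documents give no hazard ratio for site, so none is computed. Only the direction is available, from the Background.

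8. **Effect on sample size.** Correcting the labels leaves the 1:1 ratio, the target hazard ratio of 0.63 and the total of 182 unchanged.

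**The case against.** The strongest reply is that the labels are two parenthetical descriptions, probably left over from other wording. No sentence instructs anyone to place a catheter in the forearm. The instructions that staff would carry out are in the next paragraph, and they are clear: research staff direct the inserter above the fossa, and the arm determines the length. On that reading there is no confounding, the analysis and sample size are untouched, and the matter is editorial.

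Much of this stands. Left-over wording is the likeliest explanation, though that is an inference. The strict contradiction is with the site instruction rather than with the length definition. The 91 of 182 is only the size of one arm, and the 0 to 100 points are bounds that follow from the assumed f, so neither is evidence of harm. The direction of bias rests on one general sentence in the Background, which does not compare forearm with upper arm by name.

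It is also fair to ask whether a departure could be detected. Initial Assessment lists insertion location and distance from the fossa as data items, and Appendix B asks for access sites to be marked. However, the legible distance field has no indicator for above or below, and the form's figure is not shown.

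The reply does not remove the defect. The labels sit in the randomisation procedure, the envelope content is not specified, and no other section corrects them. Someone preparing envelopes from that paragraph could follow either reading.

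**Conclusion.** The concern holds, and the text must be fixed. As written, Initial Assessment cannot be followed in full for any of the 91 planned experimental patients, and its allocation sentence does not identify the factor that the trial randomises. The case rests on that ambiguity, not on demonstrated bias. The consequence ranges from none, if only the wording is wrong, to complete confounding of length with site, in the direction that favours the Ultra Long catheter, if the labels were followed throughout. The size of any bias in the hazard ratio cannot be derived from the documents.

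The conclusion assumes only that forearm means below the antecubital fossa and that the site instruction, which carries no group qualifier, applies to both arms.

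**What to change.** - Reword the allocation sentence so that it names catheter length, Ultra Long 6.35 cm or Standard Long 4.78 cm, as the randomised factor, in line with the objective, design and power statement. Have the schedule and envelopes use the same terms.
- Remove the forearm and upper-arm labels or reconcile them with the site instruction, so that a single site instruction applies to both arms. Which site that should be is for the sponsor to state.
- Have the sponsor confirm what the randomisation schedule and any envelopes already prepared actually say.
- If any patients were enrolled under this text, tabulate recorded insertion location by arm and report it with the primary result.

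The cost is a wording correction and an envelope check, with no extra patients. The tabulation uses items the plan already collects, provided that the location record distinguishes sites above the fossa from sites below it. If the form does not, add that indicator.
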